# 10.2.1 Expected AE's

The following AEs are expected disease related and/or procedural expected events:

- Bruising caused by venepuncture
- Dissociative and psychotomimetic effects, analgesia, dizziness, lack of co-ordination, unsteadiness, impaired memory and impaired concentration following infusion. Persistent effects two hours after the infusion should be reported as an SAE.
- Skin rash caused by the BACtrack Skyn device
- Increased blood pressure. Persistent increased blood pressure e.g. ≥ 220 systolic for 30 minutes should be reported as an SAE.
- Drinking lapse or relapse
- Emotional distress or anxiety caused by the psychological therapy or education sessions

Please note expected AEs should be documented in source data but are not required to be reported via the REDCap eCRF unless they meet the definition of an SAE. All unexpected AEs should be reported in both the source data and REDCap eCRF.

# 10.3 Reporting serious adverse events

Any event that meets the protocol definition of an SAE must be reported to ExeCTU and the Sponsor **within 24 hours** of the PI, designee or research team becoming aware of the event by completing an SAE eCRF in REDCap. In the even of a death a death eCRF should also be completed in REDCap.

ExeCTU and the Sponsor will be notified by email whenever a new SAE eCRF entry has been completed.

For each SAE the following information will be collected:

- Full details in medical terms with a diagnosis, if possible;
- Event duration (date of onset and date of resolution);
- Seriousness criteria;
- Causality, in the opinion of the PI (or designee);
- Action taken;
- Outcome;

In addition to the above, the following details will be collected for each SUSAR/RUSAE:

- Relevant medical history;
- Concomitant medications;
- Treatment for SUSAR/RUSAE;
- Relevant diagnostic tests.

All SAEs must be reviewed and signed by a Principal Investigator (PI) or designated representative.

It is the PI or designated representative responsibility that all SAEs/SARs/SUSARs/RUSAEs are followed up until the final outcome is reached or up to the end of the trial. All follow-up information should be entered into the eCRF as soon as the PI or designated representative becomes aware of the outcome. Ongoing SAEs/SARs/SUSARs/RUSAEs at the end of the trial will be followed up by the participant's GP and/or the routine clinical care team until discharge.

# 10.3.1 Reviewing serious adverse events

The Chief Investigator (CI) or designated representative will review all reported SAEs to assess relatedness, and where related, assess expectedness to the IMP against the RSI. All serious events judged as related to the intervention (therapy/education) will be considered unexpected i.e. RUSAE. The CI is not allowed to downgraded a PI's assessment of causality.

Sites should respond as soon as possible to requests for further information by the CI or designated representative required for the final assessment of the SAE.

In the event of a SUSAR or RUSAE, the Sponsor or delegate will take responsibility for unblinding the participant, prior to the submission of the SUSAR to the MHRA and the REC. Investigators will only

receive information on the results of the unblinding if it is judged necessary for the safety of the participant.

### 10.3.2 Expedited reporting of SUSARs

If an SAE is identified as related to the IMP and unexpected by the CI or designated representative the sponsor will be notified within 24 hours. It will be reported by the Sponsor or delegate to the MHRA and REC within the required expedited reporting timelines. SUSARs that are fatal or life-threatening must be notified to the MHRA and REC within 7 days of the CTU being notified. Other SUSARs must be reported to the REC and MHRA within 15 days after the CTU has learned of them. All other recruiting sites will be informed of the SUSAR by the Sponsor or delegate.

# 10.3.3 Expedited reporting of RUSAEs

If an SAE is identified as related to the therapy/education and unexpected by the CI or designated representative the Sponsor will be notified within 24 hours. It will be reported by the Sponsor or delegate to the REC within the required expedited reporting timelines. RUSAEs must be reported to the REC within 15 days after the CTU has learned of them. All other recruiting sites will be informed of the SUSAR by the Sponsor or delegate.

# 10.3.4 Chief Investigator responsibilities

The CI or designated representative are responsible for oversight of the safety of participants in the trial, including an ongoing review of the risk/benefit. The CI will review SAEs causality using their medical judgement and review all SARs for expectedness using the RSI in a timely manner. The CI will assign Medical Dictionary for Regulatory Activities (MedDRA) coding to all reportable safety events.

#### 10.4 Safety reporting

#### 10.4.1 Development Safety Update Report (DSUR)

A DSUR will be provided to the REC and MHRA by the Sponsor or delegate at the end of each reporting year. The CI (or designated representative) in collaboration with the Sponsor (or delegate) will prepare all relevant information for the DSUR. The CI will review the clinical sections and provide

REDACTED Version 8.0, 18/JUN/2024; IRAS ID: 1008179 MORE-KARE protocol Page 77 of 105

final sign off prior to submission. In the event of a disagreement between local assessment and CI review, local assessments will not be overruled, but the CI may add comments prior to expedited reporting.

# 10.4.2 TSC

In accordance with the TSC charter, the TSC will periodically review blinded, pooled safety data and liaise with the DMC regarding safety issues.

# 10.4.3 DMC

In accordance with the DMC charter, the DMC will periodically review unblinded safety data for each treatment group separately to determine patterns and trends of events, or to identify safety issues that would not be apparent on an individual case basis.

# 10.6 Pregnancy reporting

In the event of a pregnancy occurring during the trial, this must be reported using an ExeCTU pregnancy eCRF within 24 hours of learning of its occurrence. Pregnancies from visit 2 until 30 days post participant last IMP infusion should be reported. If the pregnancy is not known until after this time frame, it should still be reported if conception was during this period. Any pregnancy that occurs during the treatment weeks will result in exclusion from treatment. If pregnancy occurs in a participant's partner, or a participant, a pregnant partner PIS and ICF should be supplied to the pregnant person for consideration. Consent will be sought from the pregnant individual to follow the pregnancy until the end of the pregnancy (including premature termination) to determine the outcome and status of mother and child. Any adverse outcome of pregnancy should be assessed for causality to the treatment received.

Any SAE occurring in association with a pregnancy brought to the investigator's attention after the participant has completed the trial and considered by the investigator as possibly related to the investigational product, must be promptly reported to ExeCTU.

#### 10.7 IMP Overdose

We do not envisage an overdose as infusions are prepared by pharmacy or unblinded research nurses, and then administered by a research nurse/medic within the research site. Accidental administration of 50 times the higher protocol dose constitutes an overdose. In the event of an overdose, the participant should be observed closely for signs of toxicity. Appropriate supportive treatments should be provided if clinically indicated. ExeCTU and the Sponsor should be notified within 24 hours *via* the breach reporting eCRF. Local Trust procedures on incident reporting will also be followed. Overdoses will be observed from drug charts, or an anaesthetic response in the participant. If an SAE is associated with the overdose then this will be fully described in the SAE eCRF. In the case of a ketamine overdose, the participant will be withdrawn from treatment and will be invited to attend follow up visits 9 and 10 as part of our intention to treat protocol.

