#### 3. ASSESSMENT AND MANAGEMENT OF RISK

Excellent safety and tolerability data suggest that the risks of ketamine treatment would be low. Ketamine is currently indicated as an anaesthetic agent for diagnostic and surgical procedures. The use of ketamine for this anaesthetic purpose administers higher doses (1mg/kg to 4.5mg/kg over 60 seconds) than our proposed dose of 0.8mg/kg over 40 minutes, and even at these higher doses ketamine has a very good safety profile [56]. Ketamine is suggested to be used with caution in chronic alcohol dependence and the acutely alcohol-intoxicated patient. However, this is for anaesthetic doses and our phase II study indicated better liver function following treatment. Breathalysers will be used to exclude participants currently intoxicated with alcohol.

The Summary of Product Characteristics (SmPC) states that dose reductions should be considered in alcohol dependent patients: our trial does intend to use less than the minimum clinical dose of 1mg/kg as the SmPC indication is for use in anaesthesia. The SmPC also states that abnormal Liver Function Tests (LFTs) associated with ketamine use have been reported, particularly with extended use (>3 days) or drug abuse. Ketamine will be used at a lower dose than anaesthetic levels and will only be given in 3 isolated low doses, spaced at weekly intervals. Ketamine has a very short half-life and so will be quickly eliminated from the system [57].

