# 8.7 Treatment procedures (visits 2 (i.e. baseline; 14 to 28 days after screening), visit 4 (4 to 21 days after visit 2) and 6 (4 to 21 days after visit 4))

Participants will receive a weekly phone call from site staff reminding them of their next appointment date.

**Infusion:** Randomised participants will receive either 3 infusions of ketamine (0.8mg/kg made up to 50ml with saline over 40 minutes) or 3 infusions of ketamine (0.05mg/kg made up to 50ml with saline over 40 minutes), see section 9. Infusions will be administered over three weeks. The infusion will be prepared by unblinded pharmacy staff) or delegated unblinded site staff at the trial site facility. The infusion dose will be blinded to the research medic/nurse at the trial site who will administer the infusion. The total amount of ketamine hydrochloride to be delivered will be calculated on the participant's weight (0.8 or 0.05 mg/kg). Site pharmacy (or unblinded site staff) will order ketamine and dispense per participant, added to saline (0.9%) to make up to 50ml in syringes/bags for the syringe/infusion pump. Doses will be administered using a computer-controlled syringe pump if a syringe has been prepared, or a computer-controlled infusion pump if an infusion bag has been prepared. Participants will be given the option of whether they would like to listen to non-vocal instrumental music during the infusion to block out environmental noise.

**Mindfulness Based Relapse Prevention Therapy (MBRP):** A seven session manualised intervention and accompanying workbook developed with alcohol Specialist Clinical Psychologists (the supporting documents will give the details for manual and workbook). MBRP incorporates mindfulness practices alongside traditional cognitive-behavioural relapse prevention interventions [78]. The aim of these 7 sessions is to help to reduce the risk of relapse and support participants to develop an enjoyable and meaningful life without alcohol. It focuses around two broad themes, relapse prevention and promoting wellbeing, with mindfulness practice incorporated throughout the 7 sessions. Homework assignments will be used to promote incorporation of skills and strategies introduced into participants' daily lives.

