#### 8.12 Withdrawal criteria

Participants who withdraw before Visit 2 (Baseline) will be replaced by assigning successive screening IDs to eligible participants, but after completing eligibility checks and breathalyser on visit 2, participants will be randomised and will not be replaced.

Participants have the right to withdraw at any time and there is no obligation to provide reasons for withdrawal. Participants who discontinue any aspect of the trial treatment, would still be invited to complete the follow-up visits at 3 months (visit 9) and 6 months (visit 10), unless they fully withdraw from the trial. A participant cannot choose to discontinue one element of the treatment package, i.e. if they discontinue from IMP treatment they cannot continue with therapy/education or vice versa. Participants wishing to withdraw their consent from the trial should contact a member of their site trial team to make

their wishes known. In addition, the CI and/or PI may discontinue a participant from the trial at any time it is considered necessary for any reason including:

- Ineligibility (either arising during the trial or retrospectively)
- Significant non-compliance with treatment or trial requirements e.g. If the participant misses 2 consecutive infusions, as detailed in section 9.11
- An adverse event which requires discontinuation of the trial medication or results in inability to continue to comply with trial procedures
- Disease progression which requires discontinuation of the trial medication or results in inability to comply with trial procedures
- Consent withdrawn, loss of capacity or detention under Mental Health Act
- Pregnancy, see section 10.6.
- In the case of an overdose with ketamine, the participant will be withdrawn from the trial (see section 10.7)
- Positive urine screen for ketamine after randomisation. Participants would be withdrawn from treatment but invited to continue to 3-month and 6-month follow-up.

However, all efforts will be made to maintain participants in the trial where possible and to continue assessments as intended. If treatment is stopped for longer than 7 days in this trial, then it will not be possible to resume treatment. The reason for participant withdrawal will be recorded in the withdrawal/change in participation eCRF and medical notes (or source data file if no medical notes are available) within 24 hours of the site trial team becoming aware.

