#### 9 INVESTIGATIONAL MEDICINAL PRODUCT

#### 9.1 Name and description of investigational medicinal product(s)

The product under test will be ketamine hydrocholoride either 0.8mg/kg or 0.05mg/kg; 50mg/mL or 10mg/ml injection vials/ampoules will be used.

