#### 9.6 Dosage schedules

Three infusions will be administered at weekly intervals, one each at visits 2, 4 and 6. Doses will be made up from a neutral glass vial/ampoule with rubber closure and aluminium flip-off cap containing ketamine hydrochloride. The total amount to be delivered will be calculated on the basis of the participant's screening visit weight.

Site pharmacy / unblinded site staff will order ketamine and dispense per participant, added to saline (0.9%) to make up to 50ml solution in syringes/bags for the syringe/infusion pump to infuse intravenously over 40 minutes. Doses will be administered using a computer-controlled syringe pump if a syringe has been prepared, or a computer-controlled infusion pump if an infusion bag has been prepared.

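### Section 10.7 sets overdose at 50 times the higher dose (40 mg/kg), so a several-fold preparation error without an SAE does not trigger the overdose steps; separately, 8.12 and 10.7 disagree on follow-up after an overdose

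*Protocol*

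**What the plan says.** Section 10.7 defines overdose once: "Accidental administration of 50 times the higher protocol dose constitutes an overdose". It attaches consequences to the label. The participant is observed closely for toxicity, "ExeCTU and the Sponsor should be notified within 24 hours" through the breach form, and "the participant will be withdrawn from treatment and will be invited to attend follow up visits 9 and 10". The section also says overdoses will be picked up from drug charts or from an anaesthetic response. Section 14.5 lists overdose by name among the violations to be reported immediately.

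The dose and its preparation are fixed elsewhere. Section 8.7 gives the higher arm "3 infusions of ketamine (0.8mg/kg made up to 50ml with saline over 40 minutes"; the lower arm receives 0.05 mg/kg. Section 9.6 has the drug "added to saline (0.9%) to make up to 50ml solution in syringes/bags", calculated on screening weight. Section 9.1 says "50mg/mL or 10mg/ml injection vials/ampoules will be used". Section 3 puts anaesthetic doses at 1 to 4.5 mg/kg over 60 seconds and states that "our trial does intend to use less than the minimum clinical dose of 1mg/kg".

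On what follows an overdose, section 8.12 reads: "In the case of an overdose with ketamine, the participant will be withdrawn from the trial (see section 10.7").

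**The concern.** A printed overdose threshold should catch the dosing errors that could plausibly occur. This one lies so far above the intended dose that a single 50 ml preparation can reach it only in lighter participants, and only from the stronger stock. A several-fold error, the kind that two permitted vial strengths make conceivable, falls well below it.

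What is at stake is procedural safety. For a non-SAE dosing error, prompt notice to the trials unit and Sponsor, and the decision to stop further infusions, rest on site judgement even though the protocol set out to write a rule.

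The mismatch between 8.12 and 10.7 is a separate matter and does not support the threshold point. The primary analysis uses observed data only (11.3.1). A site that follows 8.12 literally may therefore lose the day-180 outcome of a participant whom the treatment policy strategy in 11.3.3 means to keep.

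**Working it through.** **Inputs.** Higher dose 0.8 mg/kg and lower dose 0.05 mg/kg (8.7, 9.1); infusion volume 50 ml (8.7, 9.6); stock 50 or 10 mg/ml (9.1); BMI 16 to 35 permitted (7.2); anaesthetic range 1 to 4.5 mg/kg (3); 280 participants with 20% attrition (11.1). Body weights and heights below are illustrations, because the protocol gives no distribution.

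**Threshold.** The protocol prints only the multiple. In mg/kg it is 50 × 0.8 = 40. Against the top of the anaesthetic range: 40 / 4.5 = 8.9.

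**Can 50 ml hold it?** Heaviest participant in whom the threshold is reachable = (stock strength × 50 ml) / 40.
- 50 mg/ml, undiluted: 2,500 mg; 2,500 / 40 = 62.5 kg. The intended dose at that weight is 0.8 × 62.5 = 50 mg, or 1 ml, so the whole 50 ml would have to be drug instead of 1 ml.
- 10 mg/ml, undiluted: 500 mg; 500 / 40 = 12.5 kg. At the minimum BMI of 16 this is a height of √(12.5/16) = 0.88 m, so no adult.

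**Largest multiple of the intended dose that fits**, stock content / (0.8 × weight):

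| Weight | 50 mg/ml stock | 10 mg/ml stock |
|---|---|---|
| 60 kg | 2,500/48 = 52 | 500/48 = 10.4 |
| 80 kg | 2,500/64 = 39 | 500/64 = 7.8 |
| 100 kg | 2,500/80 = 31 | 500/80 = 6.25 |

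**How much of the permitted weight range lies at or below 62.5 kg** (50 mg/ml stock only; weight = BMI × height²):
- 1.55 m: 38.4 to 84.1 kg; (62.5 − 38.4)/(84.1 − 38.4) = 53%.
- 1.60 m: 41.0 to 89.6 kg; (62.5 − 41.0)/(89.6 − 41.0) = 44%.

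These are shares of a range, not of participants.

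**A five-fold error.** 5 × 0.8 = 4 mg/kg, and 4/40 = 10% of the threshold. One way it could arise at 80 kg: the intended 64 mg is 6.4 ml of 10 mg/ml stock, and the same 6.4 ml drawn from 50 mg/ml stock is 320 mg. A ten-fold error (8 mg/kg) is 20% of the threshold. In the low-dose arm a five-fold error gives 0.25 mg/kg, below the higher trial dose, and is not an overdose on any reading offered here.

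**Section 10.7 against itself.** The section expects an anaesthetic response to reveal an overdose, yet the anaesthetic range in section 3 lies far below 40 mg/kg. The infusion here lasts 40 minutes rather than 60 seconds, so equal doses need not have equal effects. Even so, the detection sign does not fit the threshold.

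**Sections 8.12 and 10.7 side by side.** One removes the participant from the trial; the other removes them from treatment and keeps visits 9 and 10. The bullet after the overdose bullet in 8.12, on a positive ketamine screen, expressly keeps the 3- and 6-month follow-up, so a site could take the difference as intended. Planned completers are 280 × 0.8 = 224, so each outcome lost is 1/224 = 0.45%.

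**The case against.** The strongest defence is that little depends on the label alone.
- Section 9.7 permits no dose modification, so any such error is a deviation, and 8.12 sends all deviations to the Sponsor.
- Section 14.5 says non-SAE drug errors may be violations, and violations are reported immediately.
- Section 10.1 makes effects persisting two hours after the infusion an SAE, and 10.3 requires SAEs to be reported within 24 hours.
- Section 14.6 covers serious breaches, and 8.12 lets the investigator discontinue anyone when necessary.
- Monitoring during the infusion does not depend on the label.

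All of this stands. A reader might infer that several-fold errors would go unseen, and the documents do not support that. What remains is that none of these routes gives a fixed 24-hour notice or a mandatory treatment stop for an error without an SAE.

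A second defence is that 10.7 does not say that nothing below 50-fold counts, and that staff who saw an anaesthetic response might apply the label anyway. They might. But that sentence concerns detection and sets no second threshold.

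A reader might also conclude that the trigger cannot operate for most permitted weights. That is not established: with 50 mg/ml stock it fails for shorter participants, as the 53% at 1.55 m shows.

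The choice of a replacement is clinical. The product characteristics and pharmacy manual are not at hand, so neither the basis for 50-fold nor the controls against mixing strengths can be judged. The 1 mg/kg figure belongs to anaesthetic dosing and is not a toxicity limit for a 40-minute infusion.

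On the second point, 8.12 refers the reader to 10.7, and its general rule invites people who stop treatment to follow-up. That lowers the risk but leaves two contradictory instructions in print.

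**Conclusion.** The point holds in limited form and should be fixed. The only printed overdose threshold is 40 mg/kg. It is out of reach for every adult with 10 mg/ml stock, and reachable with undiluted 50 mg/ml stock only at 62.5 kg or less. A non-SAE error of several-fold therefore escapes three steps tied to the label: the 24-hour notification, the automatic treatment stop and the named violation. The volume argument assumes a single 50 ml preparation. No error frequency is claimed, and neither the sample size nor the method of primary analysis is affected.

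The conflict between 8.12 and 10.7 is real and small: 0.45% of planned completers for each participant lost. Under the present threshold it would seldom arise. Lowering the threshold makes it more likely to matter, so both should be corrected together.

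**What to change.** In 10.7, replace the 50-fold multiple with a low printed threshold based on the participant's calculated 0.8 mg/kg dose at screening weight. The medical lead sets it, no higher than twice that dose (1.6 mg/kg), which still captures a five-fold error. Above 1 mg/kg, a 25% excess ((1.0 − 0.8)/0.8), is one candidate, because section 3 states the intention to stay below it. Screening weight matters: on current weight a correctly prepared dose would reach 1 mg/kg after a 20% weight loss (0.8/0.8 = 1.0).

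A dose above the threshold should trigger observation and 24-hour notification. Whether the same threshold also mandates treatment withdrawal is a clinical trade-off for the medical lead to confirm in the amendment. Use the same definition in 8.12 and 14.5.

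Separately, reword 8.12 so that an overdosed participant is withdrawn from treatment but invited to visits 9 and 10, matching 10.7 and the treatment policy estimand.

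The cost is a wording amendment, site notification, a few more breach reports and possibly a few more treatment withdrawals. Those participants would leave the per-protocol set, since 11.3.3 requires all three infusions at the allocated dose and all sessions. The change does not label an arm swap (0.8 instead of 0.05 mg/kg, 16-fold), which stays with the drug-error route in 14.5.
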